† Sentinel Safety Cohort: 6 participants within each dosing group from Cohort 1 (18-49 years of age only) will be included in the Sentinel Safety Cohort.

‡ As part of risk mitigation for enhanced COVID-19, the older age stratification (≥ 50 years) will not be allocated to this study arm.

Note: A subset of 87 participants in Cohort 2 (60 participants 18-49 years of age [18 per group in AS03-adjuvanted vaccines; 6 per group in all other study groups]) and 27 participants ≥ 50 years of age [9 per group in AS03-adjuvanted groups; 3 per group in all other study groups, with the exception of the unadjuvanted group for which there will be no older adults]), will be randomly assigned to a cellular-mediated immune (CMI) subset.

All participants will receive 1 injection of either one of the investigational study vaccine formulations or the placebo control at D01 (Vaccination [VAC] 1). Participants in Cohort 2 will receive a second injection of study vaccine formulation or placebo at D22 (VAC2).

If a COVID-19 vaccine becomes available from a company other than Sanofi Pasteur, then participants are free to receive that vaccine. Participants who receive a COVID-19 vaccine will still be followed for safety until the end of the study but will be discontinued from study intervention administration thereafter.

Enrolled participants who seek vaccination of an authorized/approved vaccine outside of the study will be encouraged to discuss this intention proactively with the study investigator and will be permitted to receive the authorized vaccine at any time. As efficacy has not been demonstrated for any of the investigational formulations under evaluation in the current study, it is not required to unblind participants to the VAT00001 study assignment prior to administration of an authorized COVID-19 vaccine.

If the participant receives the authorized/approved vaccine, this information would be collected and the participant's data up to the point of receipt of authorized/approved vaccine will be included in the primary analysis for immunogenicity and safety. Participants will continue to be followed for the duration of the study as per scheduled visits and procedures. Participants will be invited to a visit prior to receiving the vaccine and invited to provide a blood sample for immunological assessment.

The duration of each participant's participation in the study will be approximately 365 days post-last injection:

[figure not shown]

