1.3 Schedule of Activities (SoA)

Visits and procedures are detailed in the Operating Guidelines.

Table 1.1: Schedule of activities 1 (Cohort 1)

Phase I/II Study, 7 Visits, 1 Telephone Call, 1 Injection, 6 Blood Sample Time-points, Approximately 12 Months' Duration Per Participant

Visit (V) / Contact	Collection of information in the CRF	V01	V02	V03	V04	Telephone Call	V05	V06	V07 or Safety Follow-up Call§§§
Study timelines (Day [D])		D01	D09	D22	D36	D43	D113	D181	D366
Time Interval (days)			V01 + 8 days	V01 + 21 days	V01 + 35 days	V01 + 42 days	V01 +112 days	V01 + 180 days	V01 + 365 days
Time windows (days)		N/A	[+2 days]	[+7 days]	[+7 days]	[+2 days]	[+7 days]	[+14 days]	[+14 days]
Visit procedures:									
Informed consent	X	X							
Point-of-care SARS-CoV-2 antibody test		X							
Inclusion/exclusion criteria	X	X							
Collection of demographic data	X	X							
Collection of medical history	X Significant Medical History	X							
Physical examination*		X							
Pre-vaccination temperature		X							
Urine pregnancy test (if applicable) †		X							
Contact IRT system for randomization, participant number, and unique dose number allocation.	X	X							
Respiratory sample collection									Can occur at any time during the study as unscheduled visit(s)

Visit (V) / Contact	Collection of information in the CRF	V01	V02	V03	V04	Telephone Call	V05	V06	V07 or Safety Follow-up Call\$\$\$\$
Study timelines (Day [D])		D01	D09	D22	D36	D43	D113	D181	D366
Time Interval (days)			V01 + 8 days	V01 + 21 days	V01 + 35 days	V01 + 42 days	V01 +112 days	V01 + 180 days	V01 + 365 days
Time windows (days)		N/A	[+2 days]	[+7 days]	[+7 days]	[+2 days]	[+7 days]	[+14 days]	[+14 days]
Visit procedures:									
Clinical safety laboratory assessments ‡ (10 mL) (All participants)	X	X§	X						
Serum samples for Ab assays (30 mL) (All participants)	X	BL0001§		BL0002	BL0003		BL0004	BL0005	BL0006
Vaccination (VAC)	X	X							
Immediate surveillance (30 minutes)	X	X							
Diary Card provided		DC1**		DC2§§	DC3***		DC4†††	DC5†††	
Diary Card reviewed			DC1††			DC3††			
Diary Card collected				DC1‡‡	DC2‡‡		DC3‡‡	DC4‡‡	DC5‡‡
Collection of solicited injection site & systemic reactions	X	D01-D08							
Collection of unsolicited AEs	X	D01-D22							
Collection of concomitant medications	X Reportable concomitant medication	All reportable concomitant medications (including influenza vaccination)			Influenza and COVID-19 vaccinations only				

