6.5 Concomitant Therapy

At the time of enrollment, ongoing medications and other therapies (eg, blood products) should be recorded in the source document as well as new medications prescribed for new medical conditions / AEs during study participation.

Documentation in the CRF of ongoing concomitant medication(s) will be limited to specific categories of medication(s) of interest beginning on the day of first vaccination. This may include medications of interest that were started prior to the day of vaccination or stopped prior to enrollment.

Reportable medications will be collected in the CRF from the day of each vaccination to the end of the solicited and unsolicited follow-up period after each vaccination, with the exception of influenza vaccination which will be collected throughout the study.

Reportable medications include medications that impact or may impact the consistency of the safety information collected after any vaccination and/or the immune response to vaccination. Three standard categories of reportable medications are defined:

- Category 1: medications impacting or that may have an impact on the evaluation of the safety (eg, antipyretics, analgesics, and non-steroidal anti-inflammatory drugs [NSAIDs], systemic steroids/corticosteroids)
- Category 2: medications impacting or that may have an impact on the immune response (eg, hydroxychloroquine, other vaccines, blood products, antibiotic classes that may interfere with bioassays used by the Global Clinical Immunology [GCI] department or other testing laboratories, systemic steroids/corticosteroids, immune-suppressors, immune-modulators with immunosuppressive properties, anti-proliferative drugs such as DNA synthesis inhibitors)
- Category 3: medications impacting or that may have an impact on both the safety and the immune response (eg, systemic steroids/corticosteroids)

Dosage and administration route, homeopathic medication, topical and inhaled steroids, as well as topical treatments, ophthalmic and ear treatments will not be recorded. Topical analgesics should not be applied at the site of vaccination; however, if they are applied inadvertently to the vaccination site, they should be recorded as a Category 1 medication in this specific instance.

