8.4.1 Time Period and Frequency for Collecting AE and SAE Information

Immediate Post-vaccination Observation Period

Participants will be kept under observation for 30 minutes after each vaccination to ensure their safety. The post-vaccination observation should be documented in the source document.

Reactogenicity

Solicited injection site reactions will be collected from D01 to D08 after each vaccination.

Solicited systemic reactions will be collected from D01 to D08 after each vaccination.

The solicited injection site reactions and systemic reactions that are pre-listed in the diary cards and CRF, together with the intensity scales, are presented in [Appendix 10.3.5.1.1](#).

Unsolicited Adverse Events

Unsolicited AEs include unsolicited non-serious AEs and SAEs. The intensity grading scale for unsolicited non-serious AEs is presented in [Appendix 10.3.5.1.2](#).

Unsolicited non-serious AEs will be collected from D01 to D22 after each vaccination.

SAEs will be collected and assessed throughout the study, from inclusion until 12 months after the last vaccination (up to D366 for Cohort 1 and up to D387 for Cohort 2). However, before the first study intervention administration, only SAEs related to study procedures are to be collected (eg, SAEs related to blood sampling).

Medical occurrences that begin before the start of study intervention but after obtaining informed consent will not be recorded on the AE section of the CRF.

All SAEs will be recorded and reported to the Sponsor or designee immediately and under no circumstance should this exceed 24 hours, as indicated in [Appendix 10.3](#). The Investigator will submit any updated SAE data to the Sponsor within 24 hours of it being available.

Investigators are not obligated to actively seek AE or SAE after conclusion of the study participation. However, if the Investigator learns of any SAE, including a death, at any time after a participant has been discharged from the study, and he/she considers the event to be reasonably related to the study intervention or study participation, the Investigator must promptly notify the Sponsor.

Medically Attended Adverse Events (MAAEs)

MAAEs will be collected at any time during the study.

Adverse Events of Special Interest (AESIs)

AESIs will be collected at any time during the study.

See [Section 8.4.6](#) for the list of AESIs.

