9.3 Populations for Analyses

The following populations are defined:

Population	Description
Randomized	All participants with a randomized group that has been allocated by IRT
Safety Analysis Set (SafAS)	Subset of randomized participants who have received at least one injection of study intervention. Participants will have their safety analyzed according to the study intervention they actually received. Safety data recorded for a vaccine received out of the protocol design will be excluded from the analysis (and listed separately).
Full analysis set (FAS)	Subset of randomized participants who received at least 1 injection of the study intervention. Participants will be analyzed according to the study intervention group to which they were randomized.
Per-protocol analysis set (PPAS)	Subset of the FAS. Participants presenting with at least one of the following relevant conditions will be excluded from the PPAS: 
 • Participant did not meet all protocol-specified inclusion criteria or met at least one of the protocol-specified exclusion criteria • Participant did not complete the protocol-defined vaccination schedule • Participant received a study intervention other than the one that he / she was randomized to receive • Preparation and / or administration of study intervention was not done as per-protocol • Participant did not receive study intervention in the proper time window • Participant received a Category 2 or Category 3 therapy / medication / as stated in Section 6.5 • Participant with positive test results in the ELISA and/or neutralization test at baseline • Additional conditions for exclusion may be identified during the review of protocol deviations; such conditions will be documented in the Statistical Analysis Plan (SAP)
Per-protocol analysis set for immunogenicity (PPAS-IAS)	Subset of PPAS excluding participants who provided all post-dose serology samples outside the proper time window or no post-dose serology sample was drawn.
Per-protocol analysis set for CMI (PPAS-CMI)	Subset of PPAS excluding participants who provided all post-dose CMI samples outside the proper time window or no post-dose CMI sample was drawn.

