5.1 Statistical Methods

Safety, immunogenicity, and efficacy analyses will be undertaken including those data collected before the date of receiving an authorized/approved COVID-19 vaccine. Those data collected on or after receiving an authorized/approved COVID-19 vaccine will be listed separately.

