5.2.3 Per-Protocol Analysis Set

Subset of the FAS. Participants presenting with at least one of the following conditions will be excluded from the PPAS:

- Participant did not meet all protocol-specified inclusion criteria or met at least one of the protocol-specified exclusion criteria
- Participant did not complete the protocol-defined vaccination schedule
- Participant received a study intervention other than the one that he / she was randomized to receive
- Preparation and / or administration of study intervention was not done as per-protocol
- Participant did not receive study intervention in the proper time window as defined in the protocol visits.
- Participant received a Category 2 or Category 3 therapy /medication / as stated in Section 6.5 of the Protocol
- Participant with positive test results in the neutralization test at baseline.

The above conditions leading to exclusion from the PPAS may be detailed and completed if necessary following the data review. In any case, if PPAS definition is modified, the PPAS definition will be finalized before the database lock and documented in an SAP update.

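### The PPAS Category 2/3 exclusion has no date limit and conflicts on its face with keeping data up to an authorized COVID-19 vaccine; the SAP also omits the protocol's baseline ELISA exclusion without declaring it (minor)

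*SAP*

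**What the plan says.** **Exclusion for medication.** SAP 5.2.3 lists, among the conditions that remove a participant from the PPAS, "Participant received a Category 2 or Category 3 therapy /medication / as stated in Section 6.5 of the Protocol". Protocol 9.3 has the same condition ("Participant received a Category 2 or Category 3 therapy / medication / as stated in" Section 6.5). Protocol 6.5 defines Category 2 as "medications impacting or that may have an impact on the immune response (eg, hydroxychloroquine, other vaccines, blood products", followed by further examples. It makes no exception for an authorized COVID-19 vaccine.

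**Collection window.** Protocol 6.5 has reportable medications collected "from the day of each vaccination to the end of the solicited and unsolicited follow-up period after each vaccination", and excepts only influenza vaccination. Protocol 8.4.1 fixes the end of that period: "Unsolicited non-serious AEs will be collected from D01 to D22 after each vaccination". The schedules of activities add a later collection period for "Influenza and COVID-19 vaccinations only".

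**Rule on authorized vaccines.** Protocol 1.1 says that the participant's "data up to the point of receipt of authorized/approved vaccine will be included in the primary analysis for immunogenicity and safety". Protocol 5.2 footnote a, protocol 7.1.2 and SAP 5.7 repeat this. SAP 5.1 states it as a cut in the data: "Safety, immunogenicity, and efficacy analyses will be undertaken including those data collected before the date of receiving an authorized/approved COVID-19 vaccine".

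**Baseline serology.** Protocol 9.3 removes from the PPAS a participant who is positive at baseline in the ELISA, the neutralization test, or both. SAP 5.2.3 names the neutralization test only. SAP 5.7 lists the changes to the planned analyses, and this is not among them.

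**Where the sets are used.** SAP 5.2.5 places primary and secondary immunogenicity on PPAS-IAS, a subset of the PPAS, with confirmation on the FAS. Efficacy uses the FAS and PPAS-IAS.

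**The concern.** The medication condition works on the participant; the authorized-vaccine rule works on the sample. If a programmer applies the condition as written, a COVID-19 vaccine taken months after D36 removes the participant from the PPAS, and with them the D22 and D36 titers drawn before receipt. Inclusion of a valid sample would then depend on an event that followed it. SAP 5.7 says that participants may take vaccines available under emergency use authorization, so such receipt is foreseen. Results counted at the first interim could disappear from the 6-month and final tables if the PPAS is derived again.

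The ELISA omission acts in the other direction. Protocol 4.2 aims the immunogenicity data at people without evidence of prior SARS-CoV-2 exposure. Without the ELISA criterion, a participant with binding antibody but no neutralizing antibody at baseline can stay in the main immunogenicity set.

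**Working it through.** The plan gives no figure to reproduce here, so the check compares texts and then gives an illustrative size.

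**Step 1: an authorized COVID-19 vaccine taken after D36.**

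| Text | Effect on the D22 and D36 samples |
|---|---|
| SAP 5.2.3 and protocol 9.3, read with the Category 2 definition | Participant leaves the PPAS and so PPAS-IAS; both samples are lost from that set |
| Protocol 1.1, 5.2 footnote a and 7.1.2; SAP 5.7 | Both samples stay in the primary immunogenicity analysis |
| SAP 5.1 | Both samples stay; only data on or after receipt are listed separately |
| SAP 5.2.5 | The primary immunogenicity analysis is on PPAS-IAS |

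The first row contradicts the next two, and the last row shows that they concern the same analysis. SAP 5.2.3 does not refer to the keep-data rule.

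**Step 2: baseline positives under the SAP wording.** Exclusion E07 covers past infection confirmed serologically. Protocol 8.2.2.1 defines serologically confirmed infection as a positive non-Spike ELISA. The first PPAS condition removes anyone who met an exclusion criterion. A baseline anti-N positive may therefore already be removed. This is not certain, because footnote b to E07 refers to the antibody test at enrollment, which protocol 8.1 describes as a lateral flow assay. The clearest exposure is the participant who is anti-S positive, anti-N negative and neutralization negative. Protocol Table 8.1 lists three IgG ELISAs at D1 (anti-S, anti-N and anti-PanCoV), and protocol 9.3 names none and gives no cutoff.

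**Step 3: number affected (assumed rates; the documents give none).** At 10% or 50% uptake of an authorized vaccine, the literal condition removes 440 × 0.10 = 44 or 440 × 0.50 = 220 participants. Under the keep-data rule it removes none. If 1% to 5% were ELISA positive and neutralization negative at baseline, the two PPAS definitions would differ by 440 × 0.01 = 4.4 to 440 × 0.05 = 22 participants.

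**Step 4: precision of a GMT.** The multiply/divide factor of the 95% CI is 10^(t(0.975, n−1) × SD/√n). Planned group sizes are from protocol 4.2. A log10 SD of 0.3 to 0.7 is assumed.

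| Planned n | No loss | 10% lost | 50% lost |
|---|---|---|---|
| 30 | 1.29-1.83 | 1.31-1.89 (n=27) | 1.47-2.44 (n=15) |
| 90 (AS03, Cohort 2) | 1.16-1.40 | 1.16-1.43 (n=81) | 1.23-1.62 (n=45) |
| 20 (unadjuvanted) | 1.38-2.13 | 1.41-2.23 (n=18) | 1.64-3.17 (n=10) |

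In the older-adult groups of 10, the half-width t/√n goes from 0.715 SD to 0.769 SD (n=9) or 1.242 SD (n=5).

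**Step 5: one retained baseline positive.** If that participant's post-dose titer is f times the geometric mean of the rest, the GMT is multiplied by f^(1/n). For f of 3 to 30 (assumed), this is 1.04 to 1.12 at n=30, 1.01 to 1.04 at n=90, and 1.06 to 1.19 at n=20.

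**The case against.** The strongest reply is that the documents already settle the first part. The keep-data rule was written for exactly this event, names the primary immunogenicity analysis, and is more specific than the general medication condition. SAP 5.1 applies its cut to all analyses, so SAP 5.2.3 need not repeat it. The condition also points to protocol 6.5, whose collection window could be read as its time limit; later receipt would then not trigger it.

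Both readings are plausible, and either would remove the conflict for later receipt. Neither is stated in 5.2.3. Section 6.5 governs what the CRF collects, not who is excluded, and the schedules go on collecting COVID-19 vaccinations after that window.

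On the ELISA, SAP 5.2.3 does allow the PPAS definition to be modified. It requires the change to be documented, and the visible text documents none. Protocol 9.3 foresees additional exclusion conditions, not removal of one. It is also fair to say that choosing an assay and cutoff after a partial lock and group-level sponsor unblinding carries its own risk of bias. This bears on how the repair is made.

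A reader might infer that valid D22 and D36 data will be lost, or that the formulation choice was distorted. The documents support neither. The FAS has no medication exclusion, so with the SAP 5.1 cut it keeps the samples drawn before receipt. SAP 5.4 confines dose selection to the first interim. A reader might also infer that previously infected participants in general stay in the PPAS; E07 with the first PPAS condition may already remove anti-N positives.

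**Conclusion.** Both inconsistencies are present in the text. The medication condition, taken literally, contradicts the rule that keeps data up to receipt, and 5.2.3 does not say which prevails. The baseline ELISA exclusion of protocol 9.3 is missing from SAP 5.2.3, and the visible SAP does not declare it; part of the SAP file is not available, so a declaration there cannot be ruled out.

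Severity is minor. All analyses are descriptive, immunogenicity is confirmed on the FAS, formulation selection used the first interim, and SAP 5.1.2.4 says the formulation is no longer investigated. At 10% loss the change in precision is small for groups of 20 to 90; it becomes appreciable at 50% loss or in the groups of 10. These sizes rest on assumed SD, uptake and titer ratios. They apply only if the literal reading is programmed, and they are not forecasts.

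**What to change.** Use the documented SAP update that 5.2.3 already provides for, before the next lock, with a matching clarification in protocol 9.3.

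1. State in 5.2.3 that receipt of an authorized or approved COVID-19 vaccine does not by itself exclude a participant from the PPAS, and that samples on or after the receipt date are censored as in SAP 5.1. The other PPAS conditions stay as they are.
2. Align the baseline criterion with protocol 9.3. Name the SARS-CoV-2 ELISA (anti-S, anti-N or both) and use a cutoff set by the laboratory without reference to trial results. If the removal was intended, declare and justify it in SAP 5.7 and show results for both versions of the set.

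The cost is a few sentences in each document and a date condition in the dataset program. COVID-19 vaccinations are already recorded and the baseline ELISAs are already planned, so no new samples are needed. A few baseline ELISA positives may leave the PPAS; they remain in the FAS. Because the update follows a partial lock and group-level sponsor unblinding, it should record when and on what basis the assay and cutoff were chosen.

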5.2.3.1 Per-Protocol Analysis Set for immunogenicity (PPAS-IAS)

Subset of PPAS excluding participants who provided all post-dose serology samples outside the proper time window or no post-dose serology sample was drawn

For participants with just part of expected post-dose serology samples outside the proper time window or without a valid test result, participants will be kept in PPAS-IAS and only samples within the time window and with a valid result will be included in immunogenicity analyses.

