The maximum amount of blood collected from each participant over the duration of the study, including any extra assessments that may be required, is not planned to exceed 340 mL (cumulative total) (see [Table 8.1](#)). Repeat or unscheduled samples may be taken for safety reasons or for technical issues with the samples.

Table 8.1: Blood sampling per visit

N=440	D1	D09	D22	D30	D36	D113/D134	D181/D202	D366/D387
Vaccination	X		X*					
Safety Labs	Cohorts 1 and 2	Cohort 1 only		Cohort 2 only				
Sera (N=440)	BL0001		BL0002		BL0003	BL0004	BL0005	BL0006
SARS CoV2 Microneut	X		X		X		X	X
Anti-S IgG ELISA	X		X		X		X	X
Anti-N IgG ELISA	X		X		X	X	X	X
Anti-PanCoV IgG ELISA	X							
PBMC/CMI (N=87)	MC0001*		MC0002*		MC0003*			
Whole Blood (N=87)	WB0001*		WB0002*		WB0003*			
COVID PCR on respiratory sample †	Illness visit							
POC Rapid Test ‡	X							

* Cohort 2 only

† 1 swab per illness visit; until day 366/387

‡ Test at site

Guidance and information for the sample collection, preparation, storage, and shipment are provided in the Operating Guidelines.

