9.1 Statistical Hypotheses

All analyses will be descriptive; no hypotheses are planned to be tested.

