5.1.2.2 Statistical Methods for Secondary Immunogenicity Objectives

For descriptive purposes, the statistics presented on [Table 5.1](#) will be produced.

Immunogenicity analyses will be performed in those BL collected before receiving an authorized/approved COVID-19 vaccine. Immunogenicity data after receiving an authorized/approved COVID-19 vaccine will be listed separately.

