5.1.2.4 Statistical Methods for Secondary Efficacy Objectives

The efficacy profile of the study vaccine candidate will be investigated with collected COVID-19 cases of efficacy endpoints including virologically-confirmed COVID-19-like illness and serologically-confirmed SARS-CoV-2 infection. Efficacy analyses will be performed on COVID-19 cases collected before receiving an authorized/approved COVID-19 vaccine. COVID-19 cases before, on and after receiving an authorized/approved COVID-19 vaccine will be listed. As the vaccine formulation used in VAT00001 is no longer investigated further and the number of COVID-19 cases collected before receiving an authorized/approved COVID-19 vaccine would be limited, planned efficacy analyses might not be performed for the final analysis.

Correlates of risk

To evaluate the correlate of risk of the collected COVID-19 cases including virologically-confirmed COVID-19-like illness and serologically-confirmed SARS-CoV-2 infection, logistic regression models will be conducted to investigate the relationship of COVID-19 cases defined above and immunogenicity responses measured by neutralization assay and ELISA. In addition, Other explanatory/independent variables under consideration are intervention groups ([vaccine, placebo]; [low-dose, high-dose, placebo]). Separate models will be performed for different consideration of intervention groups. The log10 value of neutralizing antibody titers at D36 for cohort 2 and D21 for cohort 1 are the main immunogenicity responses for this analysis. In case the majority of participants have below LLOQ neutralizing antibody titers in the placebo group, the value of below LLOQ will be treated as ½ LLOQ. Alternatively, the antibody titers of immunogenicity responses will be categorized as a discrete variable by quantile. Dose-response curve will be modeled based on the analyses in a Bayesian manner.

Vaccine efficacy

Vaccine efficacy (VE) will be assessed with the collected COVID-19 cases. The VE will be estimated as follows:

$$VE = 1 - \frac{C_v/N_v}{C_p/N_p}$$

where

- C_v and C_p are the numbers of COVID-19 cases meeting the considered secondary endpoint definition in the vaccine and placebo groups, respectively;
- N_v and N_p are the numbers of subjects in the vaccine and placebo groups, respectively.

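### The blood sample offered before an outside COVID-19 vaccine has no place in the schedule, no named assay and no analysis rule, and the undated Category 2 exclusion can remove the same participants from PPAS-IAS

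*SAP*

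**What the plan says.** For participants who take an outside COVID-19 vaccine (switchers below), the synopsis says: "Participants will be invited to a visit prior to receiving the vaccine and invited to provide a blood sample for immunological assessment". It adds that their data from before that vaccine belong in the primary immunogenicity and safety analysis, and that scheduled visits and procedures continue. Protocol 7.1.2 repeats these two statements but not the blood sample.

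The SAP agrees on the cut-off. Section 5.1 analyses data collected before the outside vaccine and lists the rest. Section 5.1.2.2 says "Immunogenicity analyses will be performed in those BL collected before receiving an authorized/approved COVID-19 vaccine", and 5.1.2.4 says "Efficacy analyses will be performed on COVID-19 cases collected before receiving an authorized/approved COVID-19 vaccine". For the main immunogenicity set, however, SAP 5.2.3.1 states that "only samples within the time window and with a valid result will be included in immunogenicity analyses". SAP 5.2.5 repeats the immunogenicity analyses on the FAS.

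Protocol 6.5 names other vaccines among Category 2 medications. Protocol 9.3 and SAP 5.2.3 exclude from the PPAS any participant who received a Category 2 medication, with no date limit.

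Protocol Section 8 sets a maximum of 340 mL of blood per participant, "including any extra assessments that may be required". On unscheduled draws it says: "Repeat or unscheduled samples may be taken for safety reasons or for technical issues with the samples".

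**The concern.** Antibody persistence at D181/D202 and D366/D387 and serologically confirmed infection are secondary endpoints, and outside vaccination threatens both. A sample taken just before it is the natural protection: it is the last serum unaffected by another spike vaccine. The synopsis provides for that sample, but nothing downstream picks it up. No table names it, no assay is assigned to it, and no rule places it in an analysis. The main immunogenicity set keeps only samples inside a visit window, and the Category 2 rule may remove the whole participant first.

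If the plan is followed as written, serum is taken from participants for a stated immunological purpose and may contribute nothing. The persistence summaries then rest on those who did not take an outside vaccine, a self-selected group.

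**Working it through.** **1. Where the sample appears.** It is in the synopsis. It is absent from SoA Tables 1.1 and 1.2 (six serum time-points each), from Table 8.1 (BL0001 to BL0006), from protocol 7.1.2, and from the SAP, including the list of changes in 5.7. Section 8 names only safety and technical reasons for unscheduled draws.

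**2. What a switcher keeps.** Table 8.1 schedules, from D36 on:

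| Sample | Day (Cohort 1 / Cohort 2) | Neutralization and anti-S | Anti-N |
|---|---|---|---|
| BL0003 | D36 | yes | yes |
| BL0004 | D113 / D134 | no | yes |
| BL0005 | D181 / D202 | yes | yes |
| BL0006 | D366 / D387 | yes | yes |

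- Switch after D36 and before D181/D202: the last scheduled clean titre is D36. The next scheduled titre is 181 − 36 = 145 days later (Cohort 1) or 202 − 36 = 166 days later (Cohort 2), and by then it follows the outside vaccine.
- Switch after D181/D202: the clean D181/D202 titre is kept and D366/D387 is lost.
- A pre-switch sample inside the V05 window (+7 days: D113 to D120, or D134 to D141) is in window, but Table 8.1 assigns only anti-N to that visit.

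**3. Infection.** Protocol 9.4.3.2 counts a negative-to-positive anti-N change at any sample after baseline, so the definition would accept the pre-switch sample. No document says the sample is tested for anti-N. Untested, a conversion since the last scheduled bleed first shows at a post-switch bleed, where SAP 5.1.2.4 only lists it. The gaps between scheduled anti-N bleeds after D36 are 113 − 36 = 77 or 134 − 36 = 98 days, then 181 − 113 = 202 − 134 = 68 days, then 366 − 181 = 387 − 202 = 185 days.

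**4. The SAP rules side by side.** Sections 5.1 and 5.1.2.2 bring the pre-switch sample in. Section 5.2.3.1 keeps it out of PPAS-IAS analyses unless it falls in a window. The endpoints are fixed to named days (protocol Table 3.1; SAP 5.1.1.4), and no rule maps an unscheduled sample to a day. SAP 5.1.3 describes a last available titre, but the one before infection, not before an outside vaccine. Ahead of all this, the undated Category 2 exclusion, read literally, removes the switcher from PPAS and PPAS-IAS, D22 and D36 included. That contradicts the statement that data up to receipt enter the primary analysis.

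**5. Blood volume.** Inputs from SoA Tables 1.1 and 1.2: serum 30 mL × 6 and safety laboratory 10 mL × 2 for everyone; CMI 40 mL × 3 and TruCulture 4 mL × 3 in the 87-participant subset. The point-of-care test volume is not stated and is left out.

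- CMI subset: 180 + 20 + 120 + 12 = 332 mL, consistent with the 340 mL maximum, leaving 340 − 332 = 8 mL.
- The other 440 − 87 = 353 participants: 180 + 20 = 200 mL, leaving 140 mL.

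The volume of the extra draw is not stated:

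| Extra draw (assumed) | CMI subset (87) | Others (353) |
|---|---|---|
| 5 mL | 337 | 205 |
| 8 mL | 340 | 208 |
| 9 mL | 341 | 209 |
| 20 mL | 352 | 220 |
| 30 mL (as other serum draws) | 362 | 230 |

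At 30 mL a CMI participant stands at 302 + 30 = 332 mL after D202 and passes 340 mL only when D387 is drawn. One missed 30 mL draw brings the total back to 332 mL.

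**The case against.** The strongest reply is that this is an unspecified sample, not an excluded one. The window sentence in SAP 5.2.3.1 opens with participants who have some of their expected post-dose samples out of window, so it is arguably about scheduled samples only. Section 5.1.2.2 analyses samples taken before the outside vaccine, the FAS has no stated window rule, and sample-handling detail is left to Operating Guidelines that are not available here. SAP 5.2.3 also lets the PPAS conditions be detailed after data review. The study is descriptive ("All analyses will be descriptive; no hypotheses are planned to be tested"), and SAP 5.1.2.4 warns that efficacy analyses may not be run at the final analysis.

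Much of this stands, and it limits what can be claimed. A reader might infer any of the following; the documents do not support them:

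- *The sample is discarded outright.* No text says so. What is missing is an assay and a rule giving it a place, on the FAS as well as on PPAS-IAS.
- *Switchers lose their only clean anti-N result.* Scheduled anti-N results at D22, D36 and D113/D134 survive if taken before the switch.
- *Every switcher loses the persistence titre.* Those who switch after D181/D202 keep that one.
- *The extra draw breaks the 340 mL maximum for everyone.* It can do so in at most 87/440 = 19.8% of participants, and conditionally.
- *Using the sample would restore precision at D181/D202.* The loss of numbers there comes from switching itself.

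What does not stand is that the existing text suffices. SAP 5.1.2.2 does not say at which time-point an unscheduled sample is summarised, and the FAS analyses use the same named days.

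**Conclusion.** The point holds as a gap with a limited but real effect. An out-of-window pre-switch sample has no assay and no analysis, despite SAP 5.1 and 5.1.2.2. The cost falls on participants who switch after D36 and before D181/D202, who have no scheduled clean neutralizing or anti-S titre after D36, and on any anti-N conversion between the last scheduled bleed and the switch, a stretch of up to 185 days. The number of switchers is not given, so the number affected cannot be stated.

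The Category 2 conflict rests on a literal reading of an undated exclusion. On that reading it reaches further than the window rule, because it also takes out D22 and D36.

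The 340 mL conflict is confined to the 87 CMI participants, needs a draw above 8 mL, and assumes that all other draws are completed. At an assumed 30 mL the total is 362 mL, 22 mL over. The other 353 would reach 230 mL.

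**What to change.** 1. Add the draw to SoA Tables 1.1 and 1.2 and to Table 8.1 with a sample number, a volume, and neutralization, anti-S and anti-N assays.
2. State in SAP 5.2.3.1 that the window rule does not apply to this sample. Report by group, on the FAS and PPAS-IAS, the GMT and fold-rise at the last sample before the outside vaccine, with days since last injection. Keep this as a separate summary, not pooled with D181/D202 or D366/D387.
3. Make the Category 2 exclusion for an outside COVID-19 vaccine apply only from the date of receipt, in protocol 9.3 and SAP 5.2.3. Without this, item 2 has no effect on PPAS-IAS.
4. Test the sample for anti-N, so that the existing definition in protocol 9.4.3.2 counts a conversion as infection before the switch. No new definition is needed.
5. Reconcile the 340 mL figure with the extra draw for the CMI subset.

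Running neutralization and anti-S on BL0004 in switchers alone is tempting but not advised: the group is selected after randomization and non-switchers would have no D113/D134 comparator.

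The cost is table rows, a few sentences of SAP text, and assays on serum the protocol already invites participants to give. The drawback is that the samples fall at varying days after injection, so the summary is supplementary and must be read with that time shown.
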